### ONLY A SMALL PROPORTION OF CANCER PATIENTS SUCCEEDED AT QUITTING SMOKING

The information from the Roswell Park study would suggest that approximately 30-40% of smokers attempt to quit at or around the time of their cancer diagnosis. A recent publication from a large, well-funded cessation service at Sloan-Kettering offering intensive cessation support, found that of over 4500 tobacco user referrals, 3430 (75%) were unreachable or refused cessation assistance. Of the over 1000 enrolled in the service, about 25% did not complete the protocol, 25% either died or were lost to follow-

up, and 43% reported no tobacco use at 6 months. In summary, the data from a large cessation service at a major cancer center suggest that these state-of-the art programs benefit only about 10% of smokers with cancer. This is, again, consistent with the findings above that suggest these individuals are heavily addicted and relatively refractory to cessation treatment, leaving about 90 percent who continue to expose themselves to smoke-derived carcinogens during the course of their therapy.

[figure not shown]
The Sloan-Kettering program assessed e-cigarette use among patients trying to quit smoking and found that as many as half of these patients were experimenting with e-cigarettes during 2013, but that e-cigarette use did not affect successful quit rates. This is becoming a common finding in population studies of e-cigarettes, in part because people receive mixed messages from the public health community regarding whether these products represent an appropriate substitute for smoking. In the present study, we will test the appeal and toxicity of e-cigarettes in smokers with cancer.

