## NICOTINE DELIVERY

Much of the nicotine from cigarettes is delivered to the brain by arterial circulation within seconds of puffing on the cigarette. This is one of the reasons for high abuse liability for cigarettes. Nicotine delivered from the oropharynx (e.g., when smokeless or nicotine gum is used) enters the venous blood and passes through the liver before going to the brain. This not only delays its delivery to the brain, but it lowers the dose because some of the nicotine is changed to cotinine in the liver. For e-cigarette aerosols, about half the nicotine absorbed is delivered through the alveoli, with the other half being delivered to the venous circulation through absorption from the oropharynx and bronchial tree. Delivery of nicotine is improving as e-cigarette manufacturers improve design. First generation e-cigarette devices, released between 2008 and 2010, delivered nicotine primarily to the mouth and oropharynx and could not product plasma nicotine concentrations equivalent to cigarettes (blue line in Figure 4 below).

[figure not shown]
Nicotine absorption from new generation devices (produced after 2010, red line in Figure 4) are able to equivalent levels of plasma nicotine, but only after 20-30 minutes of puffing. However, nicotine delivery from e-cigarettes has been shown to improve with practice, and more recent studies find that experienced users of some products can quickly deliver cigarette-like nicotine doses.

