offered participation in the study, and we will confirm eligibility. The mailing will include: A letter from their oncology group at NCCC, the brochure for their state quit line, a handout about the study, and a paper to return to us in a postage-paid envelope. If they return the paper to us requesting a referral to the quit line we will notify the D-H smoking cessation specialist. He/She will then process the referral to the quit line in EDH. The patient will then be contacted directly by the quit line. We will also provide them with their state smoking cessation help-line numbers. If they return the paper to us indicating they do not wish to quit and would like more information regarding the study, a coordinator will contact them.

Once enrolled, participants will receive the e-cigarette product described below, will be instructed on use of the e-cigarette, and given a supply that is approximately equivalent to their current nicotine intake. They will be told that e-cigarettes are theoretically safer than cigarettes, and that this trial aims to test how appealing the product is for smokers not willing to quit consuming nicotine.

We have opted to use e-cigarette products produced by Halo, a US manufacturing company that emphasizes the purity of its products and its approach to quality control in the manufacturing process. Patients will be given Halo Triton, which uses a leak-proof refillable tank system that has had a recent technological update. The patient will be shown how to fill the tank and will be observed filling it. Those not able to manage the tank refill will be given Halo G6 leak proof prefilled cartomizers (the part of the e-cigarette that contains the nicotine solution and the heating filament); these can be substituted for the tank on the Triton battery. The starter kit that will be distributed to patients is illustrated in Figure 6.

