### Exclusion Criteria:

- 1) Cancer surgery planned in the next 9 weeks
- 2) Treatment with radiation planned for the next 9 weeks
- 3) Actively trying to quit smoking, or planning to in the next 30 days. (If a subject reports that they plan to quit smoking in the next 30 days, we will call them after the 30 days to see if they are still trying to quit.)
- 4) Any use of e-cigarettes in the past 30 days
- 5) Pregnant or trying to get pregnant

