## STUDY TIMELINE AND FOLLOW-UP

The trial is designed to allow for patient visits every 3 weeks for 12 weeks. The coordinators will work with the participant and the participants' medical care teams to schedule and conduct the visits. We will contact enrolled subjects for follow-up at 6 and 12 months after enrollment. Each time, we will attempt to contact the subjects 3 times by phone over a period of 3 weeks. During the call the subject will be asked if they are still using an e-cigarette, what brand they are using, what concentration of nicotine they use, how many times a day they use it, and how often they currently smoking any combustible tobacco products.

Participants will receive free e-cigarette products for the first 9 weeks of the trial and \$20 for each visit (\$100 total). Participants that travel more than 20 miles one-way for a study-only visit (no other appointments scheduled on the day of their study visit) will be given a \$10 gas card.

Time	Baseline	3 weeks	6 weeks	9 weeks	12 weeks
Activity	Consent; survey; ecig instruction; urine; CO	Survey; ecig refill; urine; CO	Survey; ecig refill; CO	Survey; qualitative interview; urine; CO	Survey; CO
Compensation	\$20	\$20	\$20	\$20	\$20

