**Toxicity Assessment:** Our measures of toxicity, urine NNAL, 1-HOP and CO2 will be compared between the baseline and 9-week assessments via paired t-test. For NNAL, assuming a standard deviation of change in this measure of 3.8 pmol/mg creatinine (as was seen in Joseph et al. 2008), with 40 participants, this test will have 80% power at the two-sided 0.05 significance level to detect a change from baseline of 1.7 pmol/mg creatinine. There is not enough information available on 1-HOP to perform a test of power, so analysis of this metabolite is considered exploratory. For expired CO, assuming a standard deviation of change in this measure of 17.0 ppm, with 40 participants, a paired t-test comparing baseline to 9-week will have 80% power at the two-sided 0.05 significance level to detect a change from baseline that is 7.7 ppm. Additionally, since CO2 will be measured several times throughout the treatment period, the trajectory of change over time in this measure will be modeled via linear mixed effects models including random intercept and slope terms to account for repeated observations within individual. With repeated measurements of CO, the power for the mixed model will be greater than that of the paired t-test of change from baseline to detect this change over time.

We will also evaluate toxicity by analyzing cotinine level to assure that the adverse effect of increased cotinine (resultant from increased e-cigarette usage without similar decrease in combustible cigarettes). To do this, we will compute the number of participants with an increase in cotinine over the course of the study and consider this an adverse event. With 40 participants, confidence intervals around this adverse event percentage will be at most 0.32 percentage points. The table below gives the probability of observing at least 1 participant with an increase in cotinine given different true percentage of participants with this adverse event. For example, if the population-wide true percentage of participants with cotinine increase is 0.5%, then the probability of observing at least 1 of the 40 study participants with an increase is 0.18.

True percentage of participants with increase cotinine	Probability of observing at least 1 adverse event (increase in cotinine)
0.5%	0.18
1%	0.33
2%	0.55
5%	0.87
10%	0.99

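### The plan says without condition that the CO mixed model has more power than the paired t-test; this fails if CO falls by week 3 and then levels off with few visits missed. Separately, the NNAL test leaves week-3 urine unused

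*Combined protocol and SAP*

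**What the plan says.** The Toxicity Assessment text in Statistical Analysis and Power Considerations sets a two-time-point test first. NNAL, 1-HOP and CO (printed as CO2 in places) "will be compared between the baseline and 9-week assessments via paired t-test". With 40 participants and a two-sided 5% level, it gives 80% power for a CO change of 7.7 ppm (SD of change 17.0) and for an NNAL change of 1.7 pmol/mg creatinine (SD of change 3.8).

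A second CO analysis follows. CO is measured "several times throughout the treatment period, the trajectory of change over time in this measure will be modeled via linear mixed effects models", with a random intercept and slope for each person. The plan then states that "the power for the mixed model will be greater than that of the paired t-test of change from baseline to detect this change over time". It gives no trajectory shape, variance split, missing-visit rate or computed power for this model.

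The visit table in Study Timeline and Follow-up has CO at every visit. It has urine at baseline, at week 3 ("Survey; ecig refill; urine; CO") and at week 9. No NNAL analysis of the week-3 sample is described.

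**The concern.** Repeated measurements do not always add power. A straight line through four visits tests the average slope. If CO drops early and then stays level, the line misses part of the baseline-to-week-9 change, and the small gain in precision need not make up for it. The sentence carries no such condition.

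The documents do not settle the shape. At enrolment participants are "given a supply that is approximately equivalent to their current nicotine intake" (Study Design), which makes an early drop plausible. On the other hand, "nicotine delivery from e-cigarettes has been shown to improve with practice" (Nicotine Delivery), which suggests a gradual one.

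Two things are at stake. This pilot is meant to prepare a larger randomized trial, and the sentence could be reused there as a general rule. Under an early plateau, the fitted line would also understate the 9-week change. For NNAL, anyone without a week-9 sample drops out of the only test, even when a week-3 sample exists, and the text gives no missing-data rule.

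**Working it through.** **Inputs from the plan.** n = 40, two-sided 5% level. CO: change 7.7, SD of change 17.0. NNAL: change 1.7, SD of change 3.8. CO visits during supply: weeks 0, 3, 6, 9.

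**Assumptions not in the plan.** The shape of the fall; the share s of the change variance that comes from true person-level slopes; independent residuals; time entered as one linear term; for missing data, the rate, the pattern and the between-person SD.

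**1. The plan's own figures.** Noncentral t, 39 df.
- CO: noncentrality 7.7/17.0 × √40 = 2.865, power 79.8%.
- NNAL: 1.7/3.8 × √40 = 2.829, power 78.8%.

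Both agree with the stated 80% to within about a point.

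**2. What the straight line estimates.** With complete data the fixed slope is the mean of the per-person least-squares slopes. The centred times are -4.5, -1.5, 1.5, 4.5, with sum of squares 45. Nine times the slope is therefore

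9 × [4.5(y9 − y0) + 1.5(y6 − y3)]/45 = 0.9(y9 − y0) + 0.3(y6 − y3).

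If f3 and f6 are the shares of the fall reached by weeks 3 and 6, its mean is 7.7 × [0.9 + 0.3(f6 − f3)]. The residual variance factor is 2(0.81 + 0.09) = 1.8, against 2 for y9 − y0, so its SD is 17.0 × √(s + 0.9(1 − s)). This runs from 16.1 (s = 0) to 17.0 (s = 1).

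**3. Power with complete data** (paired t-test 79.8% throughout).

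| s | Linear fall (mean 7.70) | All by week 3 (mean 0.9 × 7.7 = 6.93) |
|---|---|---|
| 0 | 83.8% | 75.5% |
| 0.25 | 82.8% | 74.4% |
| 0.50 | 81.8% | 73.2% |
| 0.75 | 80.8% | 72.1% |
| 1 | 79.8% | 71.0% |

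For the early fall, signal to noise is 0.90 to 0.95 of the t-test's at every s. If individual changes also follow the step, power is 76-79% for s from 0 to 0.75, still below the t-test. If 60% and 90% of the fall are reached by weeks 3 and 6, the slope model has 80-83% over that range of s.

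The break-even is f6 − f3 = [√(s + 0.9(1 − s)) − 0.9]/0.3, which is 0.16 at s = 0 and 0.29 at s = 0.75. The slope model leads once more than that share of the fall lies between weeks 3 and 6.

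A simulation with REML fits (s = 0.5, 1,000 trials per case, error about 1.5 points) gave the same ordering. Early fall: 73.7% for the slope, 80.6% for the t-test. Linear fall: 82.7% and 79.8%.

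**4. Early fall with missing visits.** Loss completely at random and monotone, generalised least squares with known covariance, s from 0 to 0.75; the t-test uses completers.

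| Pattern | Between-person SD | Missing week 9 | Slope | Paired t |
|---|---|---|---|---|
| Spread over weeks 3, 6, 9 | 17 | 10% | 73-74% | 75% |
| Same | 17 | 15% | 72-74% | 73% |
| Same | 17 | 20% | 72-74% | 70% |
| Same | 17 | 30% | 70-76% | 64% |
| Week 9 only | 17 | 20% | 75-78% | 70% |
| Straight after baseline | 17 | 20% | 63-69% | 70% |
| Straight after baseline | 10 | 20% | 64-71.5% | 70% |

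The only context for the rates is a cessation service for cancer patients, of whom "about 25% did not complete the protocol". That is a different setting.

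**5. NNAL.** Paired t-test against the week-9 contrast from a visit-as-category model of weeks 0, 3 and 9, with equal correlation 0.5-0.9 between visits.

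| Missing week 9 | Paired t | Week 3 observed | Half of these also miss week 3 |
|---|---|---|---|
| 10% | 74% | 76% | 75-76% |
| 20% | 69% | 72% | 71-72% |
| 30% | 63% | 67-68% | 66-68% |

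At 20% missing with week 3 observed, the effective sample size is 33.8-34.3 against 32. Simulated type I error of the categorical model was 4.4-6.0%, highest at 30% missing, so a small-sample correction is needed.

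**The case against.** The strongest reply is that nothing turns on the sentence. The powered CO analysis is the paired t-test; the mixed model is additional, has no power figure and plays no part in the sample size. For the linear change that a random-slope model describes, the sentence is true, or at worst a tie. The failing case needs an early fall and few losses together, and the documents do not predict a plateau. All of this stands, and it keeps the point minor. It does not rescue an unconditional statement that the plan's own inputs can contradict.

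A reader might infer that the slope model always stays behind when people leave straight after baseline. It does not: at 20% missing and between-person SD 10, it reaches 71.5% against 69.9% when s = 0. The documents give no between-person SD, so no flat statement is possible.

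A reader might also infer that the straight line should be replaced for CO. That is a trade-off. With complete data a visit-as-category contrast only reproduces the t-test, and it has less power than the line if the fall is linear or dropout is late.

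On NNAL, the paired t-test is valid, the gain is small at low missingness, and week-3 urine may serve other assays. That is fair; the change is an inexpensive improvement and does not correct an error.

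**Conclusion.** The power sentence is not guaranteed and should be conditional. With complete data it holds for an approximately linear fall (80-84% against 79.8%). It fails when the whole fall comes by week 3 and CO then stays level (71-76%), where the line also understates the 9-week change by 10% (6.93 against 7.7 ppm). With missing visits the ordering depends on pattern and variance. The slope model overtakes at roughly 10-20% missing if losses are spread over visits or fall at week 9. With 20% lost straight after baseline, it is behind in most cases but not all.

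The complete-data result holds for every split between person-level slope and residual variance. The missing-data results rest on assumed rates, patterns and between-person SD. A reader might conclude that the trial is underpowered for CO or that using a mixed model is a mistake; the documents support neither, since the paired t-test and its 80% are sound. For NNAL, data already scheduled go unused when week 9 is missing, at a modest cost in power.

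**What to change.** 1. Delete the power sentence, or limit it to an approximately linear CO decline over weeks 0-9. This is a wording change only.
2. For NNAL, analyse weeks 0, 3 and 9 in a repeated-measures model with visit as a category, unstructured within-person covariance and a small-sample correction such as Kenward-Roger, and report the week-9 contrast. With complete data it equals the planned t-test. It needs slightly different code and no new samples or visits, and recovers about 1-2, 2-4 and 3-6 points at 10, 20 and 30% missing week 9.
3. For CO, keep the planned t-test and trajectory model. Optionally report the week-9 contrast from a visit-as-category model beside them, and say that it has less power than the straight line if the fall is linear (about 1-4 points with complete data) or dropout is late (for the early fall with 20% missing at week 9 only, 74-77% against 75-78%).

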### Primary outcomes:

**Appeal (H1)**—E-cigarette use and amount of e-cigarette product used per week, proportion of participants that report e-cigarette use at each assessment, satisfaction scores for e-cigarettes, and whether they continue e-cigarette use at 12 weeks (3w after end of trial). Correlation between change in e-cigarette use and change in cigarette use.

Combustible Tobacco Toxicity (H2)—Exhaled CO, urine NNAL and 1-hydroxy naphthaline (1- HOP). Because smokers are good at regulating nicotine intake, we expect no change in urine cotinine over time.

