Reviews of studies have found that this approach does not reduce the chances that a smoker will quit smoking. Moreover, smoker titrate their nicotine intake when given multiple nicotine products, such that urine cotinine levels remain the same when smokers are given a nicotine replacement product. More recent unpublished data show that introduction of e-cigarettes in smokers does not result in rises in saliva cotinine, but is associated with changes in cigarette consumption.

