HALO manufactures its e-cigarette and the nicotine solutions in the United States. The HALO solution e-cigarettes contain 0, 12, 18, 24, or 36 mg/ml nicotine. We have been advised to begin our participants with 18mg/ml and move up or down based on patient preference. E-cigarette liquid also comes in many flavors, and we have decided to allow participants to choose from four options. Halo has agreed to provide us with the names of their 4 highest selling liquids. They have shared an ingredients list with the Drs. [name] and [name] for the purposes of adverse event monitoring and in the event that our IRB members request information about the ingredients.

Figure 6. Starter kit for the Halo Triton tank.

Coordinators will assess participants at baseline and weeks 3, 6, 9, and 12. Although most of our patients are expected to have completed their therapy, the schedule is designed to integrate with return schedules for many chemotherapeutic regimens, if possible. We have considered the concern that chemotherapy could affect cigarette consumption or excretion of nicotine metabolites. According to our clinicians, the current chemotherapy regimens for these cancers are not associated with severe symptoms, such that patients rarely decrease their smoking during treatment. Nevertheless, we will assess the severity of 6 common chemotherapy side effects at each visit so that may be entered as a covariate in our analytic models. Regarding metabolites, for nicotine, the major metabolite cotinine is formed via CYP2A6 and CYP2B6 metabolism, and the traditional cytotoxic chemotherapeutic agents used in the cancer treatment are not known to affect the activity of these CYP450 /UGT enzymes significantly. Additionally, cyclical cytotoxic chemotherapy is not given every day throughout a cycle. The most well characterized carcinogens of smoking so far are NNK (4-(methylnitrosamino)1(3-pyridyl)-1-butanone) and NNAL (4-(methylnitrosamino)1(3-pyridyl)-1-butanol). These carcinogens are also metabolized by some of the same enzymes that metabolize nicotine including CYP2A6, UGT2B10, UGT1A4 and CYP2A13, so these should not be affected by most chemotherapeutic regimens.

Coordinators will assess eligibility, collect specimens, administer CO2 measurements and administer the surveys during the baseline and follow up visits.

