## OUTCOMES ASSESSMENT

Each visit will include a checklist that assesses how the participant is using the e-cigarettes and what problems he/she may be encountering with the use of the e-cigarette device. Adverse events will be assessed with a checklist for commonly occurring side effects from e-cigarettes and nicotine products. The coordinators will conduct and audio-record a 10-15 minute qualitative interview at 9 weeks soliciting perceptions about e-cigarettes to be transcribed and analyzed for common themes that could be useful in developing the larger intervention.

*Behavioral assessments:* We will use a Timeline Follow-Back Questionnaire (TLFB) to document use of cigarettes at baseline and cigarettes/e-cigarettes at baseline, 3, 6, 9, and 12 weeks. At follow up visits participants will be instructed to bring in all used and unused e- cigarettes, in order to verify reports of e-cigarette use. We will evaluate appeal with attitudinal ratings, on a 5-point Likert-type scale, e-cigarette ease of use, satisfaction, and enjoyment, and willingness to continue to purchase e-cigarettes in the future. All questionnaires are being programmed using a secure web-based system set up and maintained by the Dartmouth Bioinformatics group led by [name].

*Biomarkers of behavior:* Cigarette smoking will also be measured with exhaled carbon dioxide. We will assess expired breath CO2 using Micro Smokerlyzer meters (Bedfont Scientific), which have already been purchased for a previous study. The protocol will follow operating instructions that come with the devices, and the devices will be calibrated weekly with 40PPM CO2/air mixture. E-cigarette smoking will be measured with urine propylene glycol, the main constituent of e-cigarette aerosol. Some 40% of ingested

propylene glycol is excreted unchanged in the urine.

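### Any rise in urine cotinine counts as an adverse event, so the plan's own expected result of no change would be reported as an adverse-event rate near 50%

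*Combined protocol and SAP*

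**What the plan says.** The Toxicity Assessment paragraph (Statistical Analysis and Power Considerations) says of cotinine that "we will compute the number of participants with an increase in cotinine over the course of the study and consider this an adverse event". The preceding sentence gives the worry behind this: a rise "resultant from increased e-cigarette usage without similar decrease in combustible cigarettes". The counting rule does not carry that condition over. It also gives no minimum size, no visit and no creatinine handling for cotinine, and no other section supplies them.

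For NNAL, 1-HOP and breath CO (printed there as CO2), the same paragraph is specific: they "will be compared between the baseline and 9-week assessments via paired t-test". Cotinine has no such comparison.

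Primary outcomes states that "we expect no change in urine cotinine over time". The background on nicotine gives the reason, that smokers titrate their intake, so "urine cotinine levels remain the same when smokers are given a nicotine replacement product".

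On precision, the plan offers a table: "The table below gives the probability of observing at least 1 participant with an increase in cotinine", for true rates of 0.5%, 1%, 2%, 5% and 10%. It also states that the confidence interval will be at most 0.32 percentage points.

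**The concern.** Cotinine is a continuous measurement that varies within a person. A rule that flags every upward difference, however small, flags about half of a group in which nothing has changed on average. The plan would therefore report its own expected result as an adverse-event rate near 50%.

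The count would also mix chance rises with real ones in unknown proportion. Real individual rises and falls are quite possible with no mean change, because the Study Design section will "begin our participants with 18mg/ml and move up or down based on patient preference".

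Elsewhere the term adverse event means something different: "Adverse events will be assessed with a checklist for commonly occurring side effects from e-cigarettes and nicotine products". A biomarker event can sit beside a symptom checklist, but a reader who meets a rate near 50% under that name could take it as a safety signal or carry it into planning of the larger randomized trial that this pilot is meant to inform.

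**Working it through.** **Inputs.** From the documents: n = 40, single arm; urine at baseline, week 3 and week 9 (Study Timeline table); no change expected in cotinine (Primary outcomes); the at-least-one-event table and the 0.32 figure (Toxicity Assessment). Assumed: changes are normal, and all 40 give week-9 urine. Week 9 versus baseline is taken as the comparison because the other toxicity measures use it, Hypothesis 2 is set at 9 weeks, and week 9 is the last scheduled urine.

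**1. The plan's own figures.** P(at least 1 event) = 1 − (1 − p)^40.

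| True rate p | Recomputed | Printed |
|---|---|---|
| 0.5% | 0.182 | 0.18 |
| 1% | 0.331 | 0.33 |
| 2% | 0.554 | 0.55 |
| 5% | 0.871 | 0.87 |
| 10% | 0.985 | 0.99 |

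The table is arithmetically correct. The widest exact (Clopper-Pearson) 95% interval at n = 40 is at 20 of 40: 33.8% to 66.2%, a width of 0.324. So 0.32 is right on the proportion scale, as the Substitution assessment paragraph gives it. As 0.32 percentage points it is wrong by a factor of 100.

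**2. Share flagged by the rule.** With mean change d, in SD of change, the share with any rise is Φ(d). Ranges are the 2.5% and 97.5% quantiles of Binomial(40, Φ(d)).

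| Mean change d | Share flagged | Expected of 40 | 95% range |
|---|---|---|---|
| 0 | 50% | 20 | 14–26 |
| −0.25 | 40% | 16 | 10–22 |
| −0.5 | 31% | 12 | 7–18 |
| −1 | 16% | 6 | 2–11 |

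Even a mean fall of a full SD gives a rate above the table's top row.

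**3. What the table's rates would require.** Inverting, d = Φ⁻¹(p). Rates of 10%, 5%, 2%, 1% and 0.5% need mean falls of 1.28, 1.64, 2.05, 2.33 and 2.58 SD. With no mean change, P(4 or fewer rises of 40) = 9.3 × 10⁻⁸, about 9 in 100 million.

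**4. Sensitivity.**
- Skewed changes: if the arithmetic mean ratio is 1 and ratios are lognormal, the share rising is Φ(−s/2). For assumed log-SDs s of 0.2, 0.3, 0.5 and 0.8 this is 46%, 44%, 40% and 34%.
- Either visit: if a rise at week 3 or week 9 counts and the three values are exchangeable, baseline is the highest one time in three. The share flagged is 1 − 1/3 = 67%, or 26.7 of 40 (range 21 to 32).
- Loss to follow-up (assumed, as no rate is given): with 36 or 32 week-9 samples, the no-change count is 18 (12–24) or 16 (10–22), and the maximum interval width is 0.34 or 0.36.

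**5. Chance and real rises mixed.** Let f be the real share of the variance of change, with no mean change. The proportion of those flagged who truly rose is 0.5 + arcsin(√f)/π. For f = 25%, 50% and 75% (assumed; the documents give no split) this is 67%, 75% and 83%, so 33%, 25% and 17% of those flagged did not truly rise.

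**6. What the count can show.** Read against 50%, the exact two-sided sign test rejects at 27 or more, or 13 or fewer, of 40 (p = 0.038). It reaches 80% power at a true share of 72.2%, a mean rise of Φ⁻¹(0.722) = 0.59 SD. A paired t-test on the same data reaches 80% power at 0.45 SD (noncentral t, 39 df).

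**The case against.** The strongest reply is that the authors meant a narrower event. The sentence before the rule describes nicotine added without a matching fall in smoking, and the table treats the event as rare. On that view the event is under-defined rather than set at any rise. This is probably what was intended, but the rule as written contains no such restriction, and an analyst who follows it will flag every rise.

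Second, the 50% figure depends on symmetry and on one visit, neither of which the documents fix. That is true. The skewed and either-visit cases above run from 34% to 67%. If baseline and week-9 values are exchangeable, symmetry follows. The lowest of these figures is still more than three times the table's 10% maximum, and the either-visit reading makes the problem larger.

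Third, 50% is the right benchmark only for a zero median change. With an unchanged mean and skewed changes, the expected share is below 50%. This caveat stands and belongs beside any comparison with 50%.

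Fourth, this is a small pilot and nothing formal depends on the count. That also stands, and it limits the consequence. The variance splits and log-SDs used here are illustrations; the defect does not depend on them.

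**Conclusion.** The concern holds: the rule is wrong as written. When the result the plan expects occurs, about half of participants (20 of 40, range 14 to 26) would be reported as having an adverse event, and the planning table covers rates that this definition would almost never produce. The size rests on continuous changes centred on zero and a single week-9 comparison; the other readings checked give roughly one-third to two-thirds. The count is not wholly uninformative, since the share rising can be set against 50% if the median change is taken as the reference, but the plan presents it as an adverse-event rate. No test, stopping rule or committee decision in the documents uses it, so the harm is confined to a misleading safety summary. It should be fixed before analysis.

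**What to change.** 1. Make the main cotinine result the paired change from baseline to week 9 with a 95% confidence interval, for example as a geometric mean ratio, with creatinine handled as for NNAL, and show the individual changes. At n = 40 the half-width is t(0.975, 39)/√40 = 0.32 SD of change. For an assumed log-SD of 0.3, 0.5 or 0.8, exp(0.32 × log-SD) puts the ratio within a factor of 1.10, 1.17 or 1.29.
2. Stop calling any rise an adverse event. Report the share rising at week 9 as a biomarker change with an exact 95% interval, read against 50% with the zero-median condition stated. If a participant-level safety count is kept, define it at week 9 versus baseline with a pre-set relative threshold that the sponsor justifies from within-person and assay variation. Tabulate it beside the change in cigarettes per day from the Timeline Follow-Back questionnaire. Do not require that cigarettes did not fall at all, because the plan's worry is the lack of a similar decrease.
3. Replace the at-least-one-event table with exact 95% intervals at rates plausible for the chosen definition. For the share rising: 12 of 40, 16.6% to 46.5%; 20 of 40, 33.8% to 66.2%; 27 of 40, 50.9% to 81.4%. For a thresholded count: 2 of 40, 0.6% to 16.9%; 4 of 40, 2.8% to 23.7%.
4. Correct the precision statement to a width of at most 0.32, or 32 percentage points.

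**Cost.** A text change and a little more analysis, plus the work of justifying a threshold if the count is kept, since the documents give no cotinine SD. A threshold will miss real rises smaller than itself, which is why the mean and individual changes should be shown as well. Urine cotinine and cigarette counts are already collected, so no visits, samples or participants are added.
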